2.4.5.1 Analyses of adverse events

Generalities

The primary focus of AE reporting will be on TEAE as defined in [Section 2.1.4](#). Pre-treatment and post-treatment adverse events (including SAEs and AESIs) will be described separately.

If an AE date/time of onset (occurrence, worsening, or becoming serious) is incomplete, an imputation algorithm will be used to classify the AE as pre-treatment, treatment-emergent, or post-treatment. The algorithm for imputing date/time of onset will be conservative and will classify an AE as treatment emergent unless there is definitive information to determine it is pre-treatment or post-treatment. Details on classification of AEs with missing or partial onset dates are provided in [Section 2.5.3](#).

Adverse event incidence tables will present by SOC, HLGT, HLT, and PT, for each treatment arm, the number (n) and percentage (%) of patients experiencing an AE sorting based on results of column all. Multiple occurrences of the same event in the same patient will be counted only once in the tables within a treatment period. The denominator for computation of percentages is the safety population within each treatment arm.

Sorting within tables ensures the same presentation for the set of all AEs within the observation period (pre-treatment, treatment-emergent, and post-treatment). For that purpose, the table of all TEAEs presented by SOC and PT sorted by the internationally agreed SOC order and decreasing frequency of PTs within SOC will define the presentation order for all other tables unless otherwise specified. Sorting will be based on results of column all.

Analysis of all TEAEs

The following TEAE summaries will be generated for the safety populations.

- Overview of TEAEs by treatment arm, summarizing number (%) of patients with any
 - TEAE
 - Serious TEAE
 - Treatment-emergent AESI
 - TEAE leading to death
 - TEAE leading to permanent treatment discontinuation
- All TEAEs by primary SOC, HLGT, HLT, and PT, showing number (%) of patients with at least 1 TEAE sorted by the SOC internationally agreed order. The other levels (HLGT, HLT, and PT) will be presented in alphabetical order. This table will be presented by treatment arm
- All TEAEs by primary SOC and PT, showing the number (%) of patients with at least 1 TEAE, sorted by the internationally agreed SOC order and by decreasing incidence of PTs within each SOC. This sorting order will be applied to all other tables, unless otherwise specified. This table will be presented by treatment arm
- Number (%) of patients experiencing common TEAE(s) (PT incidence $\geq 5\%$ in any treatment group) presented by primary SOC and PT, sorted by the sorting order defined above
- All TEAEs related to IMP by primary SOC and PT, showing the number (%) of patients with at least 1 TEAE, sorted by the sorting order defined above. This table will be presented by treatment arm
- All TEAEs by maximal severity, presented by primary SOC and PT, showing the number (%) of patients with at least 1 TEAE by severity (ie, mild, moderate, or severe), sorted by the sorting order defined above. This table will be presented by treatment arm

Analysis of all treatment emergent serious adverse event(s)

- All treatment-emergent serious adverse events by primary SOC and PT, showing the number (%) of patients with at least 1 serious TEAE, sorted by the internationally agreed SOC order and by decreasing incidence of PTs within each SOC. This table will be presented by treatment arm
- Listings will be provided for all serious adverse events (SAE)s by treatment arm during on-treatment period

Analysis of all treatment-emergent adverse event(s) leading to treatment discontinuation

- All TEAEs leading to treatment discontinuation, by primary SOC and PT, showing the number (%) of patients with at least 1 TEAE, sorted by the internationally agreed SOC order and by decreasing incidence of PTs within each SOC. This table will be presented by treatment arm

Analysis of all treatment emergent AESI

- All treatment-emergent AESI by primary SOC and PT, showing the number (%) of patients with at least 1 treatment-emergent AESI, sorted by the internationally agreed SOC order and by decreasing incidence of PTs within each SOC. This table will be presented by treatment arm.

Analysis of pretreatment and posttreatment adverse events

An overview presenting number of patients with any pre-/post-treatment adverse events, serious pre-/post-treatment adverse events, pre-/post-treatment adverse events leading to death, pretreatment adverse events leading to permanent treatment discontinuation, pre-/post-treatment AESI will be displayed by treatment arm. If only few patients (<10% of randomized patients) are concerned, a global listing will be provided.

2.4.5.2 Deaths

The following summaries of deaths will be generated for the safety population by treatment arm.

- Number (%) of patients who died by study period (on-study, on TEAE period, post-study) and reasons for death summarized on the safety population by treatment received
- Deaths in nonrandomized patients or randomized but not treated patients
- TEAEs leading to death (death as an outcome on the AE case report form page as reported by the Investigator) by primary SOC and PT showing number (%) of patients with at least 1 TEAE leading to death, sorted by internationally agreed SOC order and by decreasing incidence of PTs within each SOC. This table will be presented by treatment received
- Listings of deaths will be provided. For deaths in non-randomized patients or randomized and not treated patients, a distinct listing will be provided

2.4.5.3 Analyses of laboratory variables

The summary statistics (including mean, standard deviation, median, Q1, Q3, minimum, and maximum) of all laboratory variables (central laboratory values and changes from baseline) will be calculated for each visit, last and worst value assessed during the treatment period, and presented by treatment group. For selected parameters, mean changes from baseline with the corresponding standard error will be plotted over time (at same time points) in each treatment group.

The incidence of PCSAs at any time during the TEAE period (on-treatment PCSAs) will be summarized by treatment group whatever the baseline level and/or according to the following baseline categories:

- Normal/missing
- Abnormal according to PCSA criterion or criteria

For laboratory parameters for which PCSA criterion is not defined, similar table(s) using the normal range could be provided.

Drug-induced liver injury

The liver function tests, namely Aspartate aminotransferase (AST), Alanine aminotransferase (ALT), Alkaline Phosphatase (ALP) and Total Bilirubin are used to assess possible drug induced liver toxicity. The proportion of patients with PCSA values at any post-baseline visit by baseline status will be displayed by treatment group for each parameter.

A e-DISH graph of distribution of peak values of ALT versus peak values of Total bilirubin will also be presented. Note that the ALT and Total bilirubin values are presented on a logarithmic scale. The graph will be divided into 4 quadrants with a vertical line corresponding to 3xULN for ALT and a horizontal line corresponding to 2xULN for Total bilirubin.

Listing of possible Hy's Law cases identified by treatment group (eg, subjects with any elevated ALT of >3xULN, and associated with an increase in bilirubin >2xULN) will display: ALT, AST, ALP, gamma-glutamyl transferase (GGT), total and conjugated bilirubin, prothrombin time (PT), partial thromboplastin time (PTT) international normalized ratio (INR), serum creatinine and complete blood count.

The normalization by parameter (to ≤ 1 ULN or return to baseline) of elevated liver function tests will be summarized by categories of elevation defined in the PCSA document (with following categories of normalization: normalized before last IMP dose, normalized after last IMP dose, and never Normalized. Note that a patient will be counted only under the maximum elevation category. Note: patients in the category of 'either elevated ALT or AST' are considered normalized only if both ALT and AST return to <1 ULN or to the baseline value.

The incidence of liver related AEs will be summarized by treatment group. The selection of PT will be based on SMQ Hepatic disorder.

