Appendix A Potentially clinically significant abnormalities (PCSA) criteria

**CRITERIA for POTENTIALLY CLINICALLY SIGNIFICANT ABNORMALITIES
for Phase 2/3 studies (oncology excepted)
(From BTD-009536 – Version 3.0 –24-MAY-2014)**

Parameter	PCSA	Comments
Clinical Chemistry		
ALT	By distribution analysis : >3 ULN >5 ULN >10 ULN >20 ULN	Enzymes activities must be expressed in ULN, not in IU/L. Concept paper on DILI – FDA draft Guidance Oct 2007. Internal DILI WG Oct 2008. Categories are cumulative. First row is mandatory. Rows following one mentioning zero can be deleted.
AST	By distribution analysis : >3 ULN >5 ULN >10 ULN >20 ULN	Enzymes activities must be expressed in ULN, not in IU/L. Concept paper on DILI – FDA draft Guidance Oct 2007. Internal DILI WG Oct 2008. Categories are cumulative. First row is mandatory. Rows following one mentioning zero can be deleted.
Alkaline Phosphatase	>1.5 ULN	Enzymes activities must be expressed in ULN, not in IU/L. Concept paper on DILI – FDA draft Guidance Oct 2007. Internal DILI WG Oct 2008.
Total Bilirubin	>1.5 ULN >2 ULN	Must be expressed in ULN, not in µmol/L or mg/L. Categories are cumulative. Concept paper on DILI – FDA draft Guidance Oct 2007. Internal DILI WG Oct 2008.
Conjugated Bilirubin	>35% Total Bilirubin and TBILI>1.5 ULN	Conjugated bilirubin dosed on a case-by-case basis.
ALT and Total Bilirubin	ALT>3 ULN and TBILI>2 ULN	Concept paper on DILI – FDA draft Guidance Oct 2007. Internal DILI WG Oct 2008. To be counted within a same treatment phase, whatever the interval between measurement.

CRITERIA for POTENTIALLY CLINICALLY SIGNIFICANT ABNORMALITIES
for Phase 2/3 studies (oncology excepted)
(From BTD-009536 – Version 3.0 –24-MAY-2014)

Parameter	PCSA	Comments
CPK	>3 ULN >10 ULN	FDA Feb 2005. Am J Cardiol April 2006. Categories are cumulative. First row is mandatory. Rows following one mentioning zero can be deleted.
CLcr (mL/min) (Estimated creatinine clearance based on the Cockcroft-Gault equation)	<15 (end stage renal disease) ≥15 - <30 (severe decrease in GFR) ≥30 - < 60 (moderate decrease in GFR) ≥60 - <90 (mild decrease in GFR) ≥ 90 (normal GFR)	FDA draft Guidance 2010 Pharmacokinetics in patients with impaired renal function-study design, data analysis, and impact on dosing and labeling

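### A patient with AST above 3xULN and bilirubin above 2xULN, but ALT at or below 3xULN, meets none of the SAP's stated joint liver criteria

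*SAP*

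**What the plan says.** Section 2.4.5.3 of the SAP, under drug-induced liver injury, opens by listing the tests: "Aspartate aminotransferase (AST), Alanine aminotransferase (ALT), Alkaline Phosphatase (ALP) and Total Bilirubin are used to assess possible drug induced liver toxicity". Appendix A gives ALT and AST separate rows with identical cut-offs, "By distribution analysis : >3 ULN >5 ULN >10 ULN >20 ULN".

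Three outputs combine a transaminase with bilirubin:

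- **Possible Hy's Law listing (2.4.5.3).** Selection is described by an example, introduced by 'eg': "subjects with any elevated ALT of >3xULN, and associated with an increase in bilirubin >2xULN". AST is one of the columns displayed for patients who are listed.
- **e-DISH graph (2.4.5.3).** "A e-DISH graph of distribution of peak values of ALT versus peak values of Total bilirubin will also be presented". The quadrants are formed by "a vertical line corresponding to 3xULN for ALT and a horizontal line corresponding to 2xULN for Total bilirubin".
- **Combined row in Appendix A.** "ALT>3 ULN and TBILI>2 ULN", counted within one treatment phase whatever the interval between the two measurements.

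Elsewhere in 2.4.5.3 the table on normalization of raised liver tests uses a category covering a rise in either transaminase. Patients in it are "considered normalized only if both ALT and AST return to <1 ULN" or to baseline. That table takes its elevation categories from the PCSA document, but Appendix A as shown has no either-transaminase category.

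**The concern.** The SAP treats AST as a liver-injury test with the same cut-offs as ALT, and in one table groups the two enzymes. When it looks for a raised transaminase together with raised bilirubin, AST drops out. The joint criterion is how the plan picks out possible serious liver injury in an individual patient. A patient whose transaminase signal is carried by AST alone would be counted once in the AST table and once in the bilirubin table. Neither table shows that both abnormalities belong to the same person. The safety analysis is descriptive (section 2.4.5), so recognising such a patient depends on the listings and displays.

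**Working it through.** The SAP states no figure to reproduce. The check is to apply its own cut-offs to every combination of the three tests and see where each patient type falls.

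**Inputs.** ALT 3xULN and bilirubin 2xULN come from the listing example, the e-DISH lines and the combined row in Appendix A. AST 3xULN is the lowest AST category in Appendix A.

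**Rules compared.**

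- Current: ALT >3xULN and bilirubin >2xULN.
- Extended: (ALT >3xULN or AST >3xULN) and bilirubin >2xULN.

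| ALT >3xULN | AST >3xULN | Bilirubin >2xULN | Current rule | e-DISH quadrant | Extended rule |
|---|---|---|---|---|---|
| no | no | no | no | lower left | no |
| no | no | yes | no | upper left | no |
| no | yes | no | no | lower left | no |
| **no** | **yes** | **yes** | **no** | **upper left** | **yes** |
| yes | no | no | no | lower right | no |
| yes | no | yes | yes | upper right | yes |
| yes | yes | no | no | lower right | no |
| yes | yes | yes | yes | upper right | yes |

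Two of the eight patterns meet the current rule and three meet the extended one. The only row that changes is the fourth: AST and bilirubin high, ALT not. This counts patterns, not patients.

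**Where the fourth-row patient appears as planned.**

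- Listing: the stated example is not met. Because it is only an example, the text neither includes nor strictly excludes this patient.
- Combined row in Appendix A: not met.
- e-DISH: plotted in the upper-left quadrant, where the reader sees raised bilirubin without a raised transaminase although AST is raised. The second row falls in the same quadrant, so the graph cannot tell the two apart.
- Single-parameter PCSA tables: counted once for AST and once for bilirubin, with no link between them.
- Liver event of special interest (section 2.1.4.1): defined on ALT, so it offers no AST route.

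**Number of patients.** The SAP gives no rate for this pattern. Purely as an assumption, take 1 in 1,000 to 1 in 200. Among the roughly 216 patients of Part 2 (section 1.3.2), the expected number is 216/1,000 = 0.22 to 216/200 = 1.08. In one arm of 108 it is 108/1,000 = 0.11 to 108/200 = 0.54.

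**The case against.** The best defence is that the plan is coherently ALT-based and contradicts nothing. The sentence naming the four tests is followed by how they are used, namely PCSA proportions for each parameter, and AST gets that. ALP is named in the same sentence and is also outside each joint rule. The either-transaminase category concerns when a raised enzyme has normalized, not what counts as a joint case. Appendix A comes from a sponsor standard that cites regulatory guidance and an internal working group, neither of which can be checked here. ALT alone also avoids listing AST rises of non-hepatic origin.

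Most of this stands. There is no contradiction, and whether ALT alone is an adequate convention cannot be settled from the SAP. The ALP comparison is weaker: ALP is not a transaminase and has a different cut-off in Appendix A, whereas AST has exactly the ALT cut-offs and is grouped with ALT in the normalization table.

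A reader might also infer more than the SAP supports:

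- That any patient with high AST and high bilirubin is missed. If ALT is also above 3xULN, all three joint criteria are met.
- That the AST-only patient is absent from every joint output. The e-DISH graph is not restricted to patients meeting a criterion, so the patient is plotted, though outside the joint quadrant.
- That the listing bars AST cases. Its rule is introduced as an example and is left open. This is still a weakness: ALT is all a programmer is given to code, and adding AST later would be a choice made outside the plan.

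**Conclusion.** The point holds in a narrow form. No stated joint criterion includes AST, so a patient with AST above 3xULN, bilirubin above 2xULN and ALT at or below 3xULN meets none of them, and no other output described in the liver section links the two abnormalities in one patient. Separately, the normalization table relies on an either-transaminase category that Appendix A as shown does not define.

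This is a cheap improvement to safety reporting, not an error in the plan. It does not touch the efficacy analyses or the type I error. Few or no such patients are to be expected: about one at most in 216 under the assumed range, which nothing in the SAP supports or refutes. The case for acting rests on the purpose of the listing, which is to find rare individual patients, and on the small cost.

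**What to change.** 1. In section 2.4.5.3, define the possible Hy's Law listing as (ALT or AST) >3xULN and total bilirubin >2xULN, stated as the rule and not as an example. The displayed columns stay as planned.
2. In Appendix A, add a combined row for (ALT or AST) >3 ULN and total bilirubin >2 ULN, with the same within-phase counting as the existing ALT row. Define the either-transaminase category there, so that the normalization table has a definition to point to.
3. Optionally, add an AST panel to the e-DISH graph and keep the ALT panel unchanged.

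If the sponsor prefers ALT alone, one sentence giving the reason would suffice, together with an exact rule for the listing and the missing category definition.

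The cost is one condition in the listing program, one table row and, if wanted, one graph panel. The downside is that an occasional AST rise of non-hepatic origin will be listed and dismissed on review. No data collection or patient management changes.

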2.4.5.4 Analyses of vital sign variables

The summary statistics (including number, mean, median, standard deviation, minimum and maximum) of all vital signs variables (raw data and changes from baseline) will be calculated for each time point or study assessment (baseline, each post-baseline time point, endpoint) by treatment arm. For parameters heart rate, systolic and diastolic blood pressures, the last on-treatment and worst on-treatment value will also be provided.

The incidence of PCSAs at any time during the TEAE period will be summarized by treatment arm irrespective of the baseline level and according to the following baseline status categories:

- Normal/missing
- Abnormal according to PCSA criterion or criteria

Listings will be provided with flags indicating the out of range values as well as PCSA values.

2.4.5.5 Analyses of electrocardiogram variables

The summary statistics (including number, mean, median, standard deviation, minimum and maximum) of all ECG variables (central reading values and changes from baseline) will be calculated for each time point or study assessment (baseline, each post-baseline time point, endpoints) by treatment arm.

The incidence of PCSAs at any time during the TEAE period will be summarized by treatment arm irrespective of the baseline level and according to the following baseline status categories:

- Normal/missing
- Abnormal according to PCSA criterion or criteria

Listings will be provided with flags indicating the out of range values as well as PCSA values.

2.4.5.6 Analyses of physical examination variables

Number and percentages of patients with abnormal physical examinations at any time during the TEAE period (see [Section 2.1.4](#)) will be summarized. A listing will be provided for patients with abnormal physical examination.

2.4.5.7 Analyses neurological examination variables

Number and percentages of patients with abnormal neurological examination at any time during the TEAE period (see [Section 2.1.4](#)) will be summarized. A listing will be provided for patients with abnormal neurological examination.

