1.1 STUDY DESIGN AND RANDOMIZATION

This is a two-part, multicenter, multiple-country, randomized, double-blinded, placebo-controlled study in early-stage Parkinson Disease (PD) patients carrying a GBA mutation. The study will be divided into 2 consecutive parts. Part 1 will be a randomized, double-blinded, placebo-controlled dose escalation study, utilizing a sequential cohort design. Part 1 will allow selection of the dose of GZ/SAR402671 for Part 2, a randomized, double-blind, placebo-controlled, 2-arm study of the efficacy and safety of GZ/SAR402671. Part 1 will be conducted only in selected sites (approximately 20 sites [including 4 Japanese sites]); Part 2 will be conducted at multiple sites (approximately 50). Part 2 will start after the appropriate dose for Part 2 is selected in Part 1.

In Part 1, during the screening/baseline period, from Day -60 to Day -1, patients will provide informed consent and undergo screening assessments to determine trial eligibility and undergo baseline measurements. If all eligibility criteria are met, patients will enter the trial. Part 1 will determine the safety and tolerability of GZ/SAR402671 at 4, 8, and 15 mg in early-stage PD patients carrying a GBA mutation by using a dose escalation scheme (4 weeks to assess safety and tolerability of dose and a minimum of an additional 4 weeks to further assess safety and tolerability and any potential changes in other exploratory endpoints in each dose cohort). There will be 3 sequential cohorts that will be placebo-controlled:

- Cohort 1: 4 patients (or 3 patients in Japan) on GZ/SAR402671 4 mg and 1 patient on placebo
- Cohort 2: 4 patients (or 3 patients in Japan) on GZ/SAR402671 8 mg and 1 patient on placebo

- Cohort 3: 4 patients (or 3 patients in Japan) on GZ/SAR402671 15 mg and 1 patient on placebo

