2 STATISTICAL AND ANALYTICAL PROCEDURES

2.1 ANALYSIS ENDPOINTS

2.1.1 Demographic and baseline characteristics

The baseline value is defined as the last available value obtained before or equal to the date and time of the first double-blind Investigation Medicinal Product (IMP) administration. In case of missing time of the first double-blind IMP administration and/or time of assessment, the baseline value is defined as the last available value obtained before or equal to the date of the first double-blind IMP. For patients randomized and not treated, the baseline value is defined as the last available value obtained before or equal to the date and time of randomization.

All baseline safety and efficacy parameters are presented along with the on-treatment summary statistics in the safety and efficacy sections ([Section 2.4.5](#) and [Section 2.4.4](#)).

Demographic characteristics

Demographic variables include:

- Gender (Male, Female)
- Age in years (quantitative and categorical variable : <45, [45 – 65[, [65 - 75[and ≥75 years),
- Race (White, Black or African American, Asian, American Indian or Alaska Native, Native Hawaiian or other Pacific Island, other)
- Ethnicity (Hispanic, non-Hispanic)
- Weight in kilograms (quantitative and categorical variable: <50, ≥50 and <100, ≥100)
- Body mass index (BMI) in kg/m² (quantitative and categorical variable: <30, ≥30)

Parkinson's disease history

Parkinson's disease history include:

- Time since onset of symptoms (in years)
- Time since diagnosis (in years)
- Predominance of symptom at onset (Tremor, Rigidity / Bradykinesia)
- Family history of Parkinson's disease (yes, no)

Any technical details related to computation, dates, and imputation for missing dates are described in [Section 2.5.3](#).

GBA mutations

GBA mutations will be categorized as severe GBA mutation or other GBA mutation. The list of most common mutations is provided in Appendix B.

Medical or surgical history

All medical or surgical history information in the e-CRF will be coded using the version of Medical Dictionary for Regulatory Activities (MedDRA) currently in effect at Sanofi at the time of database lock.

Alcohol Habits

Alcohol habits include:

- Frequency of alcoholic drinks in the last 12 months (Never/Occasional/At least monthly/At least weekly/At least daily)

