2.1.4.7 Neurological examination

Each neurological examination will include, but not be limited to, assessments of the patient's mental status, cranial nerves, motor system (including muscle atrophy, tone and power), deep tendon reflex, sensation, and cerebellar function.

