2.4.5.8 Analyses of ophthalmological examination variables

Number and percentages of patients with any abnormal ophthalmological examination on any eye at any time (whether present at screening or not) as well as number and percentages of patients with any new onset of abnormal ophthalmological examination on any eye during the TEAE period (see [Section 2.1.4](#)) as per investigator (site ophthalmologist) assessment will be summarized. A listing will be provided for patients with new onset of abnormal ophthalmological examination on any eye during the TEAE period.

Number and percentages of patients with any definite worsening of lens opacity on any eye as well as number and percentages of patients with any possible worsening of lens opacity on any eye during the TEAE period (see [Section 2.1.4](#)) as per central reader assessment will be summarized along with a description of lens opacity grading according to the ARLNS grading system (1). A listing will be provided for patients with worsening (definite or possible) of lens opacity on any eye during the TEAE period.

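### The neurological examination table (SAP 2.4.5.7) does not separate abnormality present before dosing from new abnormality, so it dilutes any between-arm difference

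*SAP*

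**What the plan says.** Section 2.4.5.7 contains two outputs and nothing more: "Number and percentages of patients with abnormal neurological examination at any time during the TEAE period", and "A listing will be provided for patients with abnormal neurological examination". It has no new-onset count, no worsening category and no split by baseline status.

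Section 2.1.4.7 defines the examination. Besides mental status and cranial nerves it covers "motor system (including muscle atrophy, tone and power), deep tendon reflex, sensation, and cerebellar function". Section 1.1 describes the trial as a "placebo-controlled study in early-stage Parkinson Disease (PD) patients carrying a GBA mutation", and Section 2.1.1 records tremor or rigidity/bradykinesia as the predominant symptom at onset.

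Neighbouring sections do use baseline. For the eye examination, Section 2.4.5.8 counts any abnormality and, separately, patients with "any new onset of abnormal ophthalmological examination on any eye during the TEAE period". Laboratory, vital-sign and ECG abnormalities (2.4.5.3 to 2.4.5.5) are broken down by baseline category. Section 2.4.5.9 counts worsening of BDI-II from baseline. Only the physical examination shares the gap: "Number and percentages of patients with abnormal physical examinations at any time during the TEAE period" (2.4.5.6). The common safety rules in Section 2.4.5 deal with threshold abnormalities and quantitative measurements, so they do not supply a baseline rule for a normal/abnormal examination.

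**The concern.** The disease under study produces motor signs that this examination looks for. A patient with such signs before dosing enters the count at the first examination on treatment. A cranial nerve, sensory or cerebellar deficit that develops later leaves the count unchanged, as does worsening of an existing sign. The more patients who start out abnormal, the closer both arms sit to the ceiling and the less the table can distinguish them.

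The neurological examination is a named safety endpoint in both parts (Section 2.1.4), and safety and tolerability against placebo is a secondary objective of Part 2 (Section 1.2.2.2). The drug is also required to show CSF exposure at the dose used (Section 1.1). Two similar high percentages could be read as evidence of no neurological difference when the table had little ability to show one. The same count would carry into the long-term follow-up and overall-exposure analyses, where disease progression adds to the background.

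**Working it through.** The SAP gives no figure for the examination itself. The only planned figure used here is the arm size, which turns percentages into patients. It reproduces: a difference of 4.06 with SD 10.01 is an effect size of 4.06 / 10.01 = 0.406. A two-sample t-test at two-sided 0.05 and 80% power needs 97 per arm, and 97 / 0.9 = 107.8, hence 108 as stated in Section 1.3.2.

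**Inputs**
- b, the share abnormal at baseline: not in the SAP; varied from 0% to 100%. It is taken as equal in the two randomised arms and as persisting on treatment.
- r, the share developing a new deficit on treatment: not in the SAP; assumed 5% on placebo and 20% on drug, independent of baseline status.
- n = 108 per arm.

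**Formula**

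P(abnormal at any time) = b + (1 − b) × r

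Difference between arms = (1 − b) × (r on drug − r on placebo) = (1 − b) × 15 points

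| b | Placebo | Drug | Difference (points) | Patients of 108, placebo vs drug |
|---|---|---|---|---|
| 0% | 5.0% | 20.0% | 15 | 5.4 vs 21.6 |
| 50% | 52.5% | 60.0% | 7.5 | 56.7 vs 64.8 |
| 80% | 81.0% | 84.0% | 3 | 87.5 vs 90.7 |
| 90% | 90.5% | 92.0% | 1.5 | 97.7 vs 99.4 |
| 100% | 100% | 100% | 0 | 108 vs 108 |

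For example, at b = 90%: 0.90 + 0.10 × 0.05 = 0.905 and 0.90 + 0.10 × 0.20 = 0.920.

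Other assumed rates behave the same way. At b = 90%, 5% vs 15% gives 0.10 × 10 = 1.0 point, and 10% vs 25% gives 0.10 × 15 = 1.5 points.

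**What a baseline reference recovers.** This depends on how the examination is recorded.
- By domain: a patient with a motor sign at baseline can still count as newly abnormal in, say, sensation, so new deficits in other domains become countable.
- As one overall flag: only patients normal at baseline can be newly abnormal. At b = 90% that is 0.10 × 108 = 10.8 patients per arm, with 10.8 × 0.05 = 0.54 against 10.8 × 0.20 = 2.16 new cases. A shift table would then show 5% against 20% in the informative patients and how few they are, but could not show change in the other 90%.

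**The case against.** The strongest reply is that the plan as a whole does not depend on this table. Section 2.1.4.1 defines TEAEs to include events that develop or worsen, and Section 2.4.5.1 tabulates them by arm, by system organ class and preferred term, and by severity. A new neurological deficit reported as an adverse event would appear there. Abnormal patients are listed, and motor and cognitive change from baseline is measured by MDS-UPDRS, PD-CRS and MoCA. Section 2.1.1 says baseline safety parameters are shown beside the on-treatment summaries, so a reader should see the starting rate. Safety analyses are descriptive, with no systematic testing.

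Most of this stands, and it rules out one stronger reading: that a new or worsening deficit on drug would be invisible in the trial. The documents do not support that. The reply does not rescue the table. A baseline percentage beside an on-treatment percentage shows net change, not which patients changed. A listing is not a comparison between arms. Adverse event tables depend on the investigator declaring an event, whereas a scheduled examination is there to catch what is not declared.

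A second tempting reading is that nearly every patient will be counted and both arms will sit near 100%. That is an inference from the disease and the examination content. The SAP gives no baseline rate and no rule on whether expected Parkinson signs make an examination abnormal.

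A third objection also stands: the SAP does not say that findings are recorded by domain or graded. For the physical examination it says only normal or abnormal (Section 2.1.4.6). A count of worsening may therefore not be derivable.

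The internal review that chose the Part 2 dose also looked at neurological examinations, but among much other data and in very small cohorts. Section 2.4.3.2 already fixes 15 mg, so little weight should rest on that point.

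**Conclusion.** The concern holds for this table. The any-time count mixes pre-existing with new abnormality and shrinks a between-arm difference by (1 − b). On the assumed 5% and 20% rates, half of a 15-point excess is lost at a baseline share of 50%, and 1.5 points remain at 90%. The direction follows from the definition of the count. The size rests on assumed values for b and r, on b being equal in the two arms, and on baseline abnormality persisting. At any baseline share, worsening in a patient already abnormal never registers.

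This is a weakness in one descriptive safety output. It leaves the primary and secondary efficacy analyses untouched, and it does not mean that neurological harm would go undetected elsewhere in the plan. It is worth correcting because the endpoint is named, the SAP already applies the remedy in the next section, and the change is cheap.

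**What to change.** In Section 2.4.5.7:

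1. Keep the existing count.
2. Add, by treatment arm, the number and percentage of patients with a new-onset abnormality relative to baseline, or a table of baseline status against worst post-baseline status. Use as denominator the patients with a baseline and at least one post-baseline examination. Section 2.4.5.8 is the model, since it reports both counts.
3. Present this by examination domain, and include worsening, where the collected data allow. If only one overall flag exists, use the shift table, so that the number of patients normal at baseline is visible.
4. Show baseline status in the listing.
5. Optionally, apply the same split in Section 2.4.5.6.

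The cost is a short SAP revision and one additional descriptive table, with no new assessments.
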